Research Code

Radiographic and Clinical Evaluation of Three-Dimensional Delta Plate in Internal Fixation of Mandibular Sub-condylar Fractures.

(Longitudinal Study)

Research Protocol

Submitted to the Department of Oral and Maxillofacial Surgery

Faculty of Dentistry, Ain Shams University.

**In partial fulfillment of the requirements of Masters' degree in Oral
and Maxillofacial Surgery.**

By:

[name]

**B.D.S. Faculty of Dentistry Ain Shams University
2019**

Email: [contact]

Under the Supervision of:

[name].[name]

Professor of Oral and Maxillofacial Surgery
Faculty of Dentistry
Ain Shams University

[name] [name]

Lecturer of Oral and Maxillofacial Surgery
Faculty of Dentistry
Ain Shams University

[name] [name]

Fellow of Oral and Maxillofacial Surgery
Ahmed Maher Teaching Hospital

Year of protocol registration

2023

Table of Contents

Topic	Page
I. Abstract	4
II. Background	5
III. Research Question	8
IV. Aims (Objectives)	9
V. Hypothesis	10
VI. Ethical Considerations	11
VII. Study design	13
VIII. Materials and Methods	14
• Study setting	15
• Sample Size	16
• Study Procedures	17
IX. Statistical Analysis	18
X. Funding of the Study	19
XI. References	20
XII. Arabic summary	23

I. Abstract:

Management of Sub-condylar fractures has been debatable for years, some surgeons advocate closed management if the situation permits, to avoid the complications associated with open reduction and internal fixation (ORIF). Nowadays, there are meticulous approaches and novel osteosynthesis systems that facilitate its open management but many of these systems need more research work to evaluate its efficacy.

In this study we intend to examine the efficacy of 3D delta plates from the radiographic and clinical point of view. This Single arm study will include 14 cases of trauma having mandibular sub condylar fractures, in which open reduction and internal fixation are indicated. After selecting patients according to the inclusion criteria, all patients will undergo open reduction and rigid fixation. Fracture will be stabilized using 4 hole, 2.0 mm 3-D Delta titanium plates using pre-auricular or retromandibular incision.

Postoperative clinical examination will be carried out on day three, day seven, one month and after three months. Postoperative radiographic examination will be performed immediately postoperative by CT scan.

II. Background:

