Indications for ORIF include bilateral fractures(relative), severe dislocation (> 10 degrees), other facial fractures affecting the occlusion, foreign bodies, lateral displacement of the condyle, and condyle displacement into the middle cranial fossa(11), mandibular nerve paraesthesia(12). Condylar fractures can be reached through trans -facial or intraoral approaches (13,14) .Singh et al (15) published the largest blinded, randomized controlled trial comparing open techniques with closed management; they concluded that both treatment options carry promising outcomes. However, the surgically treated group showed better results in all objective and subjective functional outcomes except for occlusion.

The gold standard osteosynthesis system is the use of two miniplates fixation secured with four screws each (16). However, some drawbacks such as; difficult accessibility that elongates operation time especially in higher fractures the use of double miniplates is associated with risk of facial nerve injury and subsequent facial nerve palsy. Moreover, the little amount of bone that is always encountered at the proximal part of the fracture (17).

Recently, Osteosynthesis devices with various shapes and sizes as single L, Y plate, or 3-D plate are used for the management of condylar fractures. Manufacturers tend to develop such systems to gain outcomes similar to that of the conventional 2 mini-plate system regarding functional stability and rigidity with less cost, less complications and less effort(17).

Several studies were conducted on three-dimensional plating systems such as Rhomboid, Trapezoid and Delta shaped plates that yielded good outcomes (17–21). One study claimed that trapezoidal condylar plate is convenient for low sub condylar fractures because of its wide dimensions, On the other hand, delta plate is suitable for both high and low sub condylar fracture. ((22–24)

The aim of this study is to evaluate the versatility of three-dimensional delta plate in reduction and fixation of this type of fracture in adult patients presented with unilateral sub-condylar fractures for primary ORIF. The results will be analyzed by radiographic assessment of proper anatomical reduction and measurement of vertical ramus height. In addition to, clinical outcomes of pain with jaw movements and measurement of all mandibular movements range.

III. Research Question:

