What are the radiographic and clinical outcomes of using three-dimensional Delta plate for primary open reduction and internal fixation of unilateral subcondylar fractures in adult patients?

PICOTS Elements:	
Patient/Problem	Adult patients presenting with unilateral sub condylar fracture, with or without concomitant facial or mandibular fractures.
Intervention	Primary ORIF using three-dimensional delta plate
Comparator	-
Outcome	Pain, posterior facial height, anatomic reduction, mouth deviation.
Time	3 months follow up
Setting	Faculty of Dentistry-Ain Shams University

IV. Aim of the Study, Research Objectives and Clinical Relevance Aim:

The aim of the study is to assess the efficacy of the delta plate in fixation of sub condylar fractures by radiographic evaluation of anatomic reduction and vertical ramus height and clinical evaluation of pain with jaw movements and range of mandibular movements.

Outcomes:

Primary outcomes: 1-Anatomic Reduction
2-Posterior Facial Height

Secondary outcomes: 1-Pain
2-Mandibular Movements.

Clinical Relevance:

Delta plate provides functionally stable osteosynthesis. In addition to, less periosteal dissection, and easier reduction and fixation of small fragments combined with the advantages of a smaller plate size, less cost and adequate stiffness (19,23).

V. Hypothesis:

Delta plate doesn't provide an added advantage over the other Osteosynthesis methods of Sub condylar fixation.

VI. Ethical consideration

Open reduction and internal fixation of sub condylar fractures is accompanied with complications such as facial nerve injury, parotid gland fistula, permanent scar, infection, pain, edema, and difficulty in mastication following surgical procedure.

Risk of Facial injury can be decreased by choosing the appropriate incision and meticulous dissection of the tissues.

Parotid gland fistula is avoided by suturing of parotid capsule or by retroparotid-retromandibular approach whenever possible.

Permanent scar is best minimized by minimal tissue trauma, suturing in layers then the skin will be sutured by Prolene 6-0, Topical antibiotics and topical silicone gel will be prescribed.

Risk of Infection is reduced by post-operative antibiotic.

Post-operative analgesics and anti-inflammatory medications will be given to control pain and edema.

Mastication force is enhanced by physiotherapy.

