All patients will undergo clinical evaluation of pain, mandible deviation on opening and closing, measurement of mandibular movements.

All patients will undergo pre-operative anesthetic evaluation which includes medical and surgical history, physical examination, investigations, risk assessment, consent and pre-medication.

Surgical Procedure:

All patients will undergo open reduction and internal fixation under general anesthesia.

The Fracture will be exposed either extraorally (submandibular or retromandibular or endaural approaches). The incision will be chosen according to the level of the fracture.

Fracture will be reduced; occlusion will be re checked then it will be fixated by 2.0 mm 3D Delta mini plates and anchored by 4 screws of 7-9 mm length.

Immediate post-operative medications:

All patients will take painkillers, anti-inflammatory, antibiotics and steroids.

Follow up:

Radiographic outcomes: The following will be measured on CT:

1-The vertical ramus height will be done by comparing the two sides from the glenoid fossa to the inferior border of the ramus on CT.

2- Accuracy of anatomical reduction detected on coronal and axial sections.

Radiograph will be taken immediately post-operative.

Clinical outcomes:

1- Assessment of pain by Visual Analogue scale.

2- Mandibular movements by a ruler:

-Lateral mandibular movement by measuring the horizontal distance between upper central teeth midline to the lower central teeth midline.

-Protrusive mandibular movement by measuring the transvere distance between upper central teeth midline to the lower central teeth midline.

-Maximal mouth opening by measuring the vertical distance between upper central teeth midline to the lower central teeth midline.

Follow up notes will be taken on day three, day seven, one month and Three months postoperatively.

IX. Statistical Analysis:

Regarding the continuous date, the T dependent test will be used to assess the statistical data. Regarding the discrete data, Chi Square test will be used to assess the statistical data significance, using SPSS Software.

X. Funding of the Study:

The research study will be self-funded by the operator. No internal or external funding will be shared in this study.

XI. References:

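### With one arm and no reference value, a paired t-test on pain and jaw movement cannot show plate efficacy, and two of these measures need tighter definition

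*Protocol*

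**What the plan says.** The Abstract describes the design: "This Single arm study will include 14 cases of trauma having mandibular sub condylar fractures". The PICOTS table in section III leaves the comparator blank. The aim in section IV is the efficacy of the delta plate, judged partly by "clinical evaluation of pain with jaw movements and range of mandibular movements". The hypothesis in section V is comparative: it sets the delta plate against other fixation methods. Pain and mandibular movements are listed as secondary outcomes; anatomic reduction and posterior facial height are primary.

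Section VIII, Pre-operative Assessment, takes the baseline: "All patients will undergo clinical evaluation of pain, mandible deviation on opening and closing, measurement of mandibular movements". Under Follow up: "Follow up notes will be taken on day three, day seven, one month and Three months postoperatively". Under Immediate post-operative medications: "All patients will take painkillers, anti-inflammatory, antibiotics and steroids". Section VI says that analgesics and anti-inflammatories are meant to control pain and edema, and mentions physiotherapy.

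The clinical outcomes list in section VIII assesses pain on a visual analogue scale, without saying under what condition it is scored. It defines one of the movements so: "Lateral mandibular movement by measuring the horizontal distance between upper central teeth midline to the lower central teeth midline". Section IX gives the test: "Regarding the continuous date, the T dependent test will be used to assess the statistical data". It does not name the pair of visits.

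**The concern.** In a single-arm study, a dependent t-test on pain or movement has the null hypothesis of no change between two visits. Fracture healing, drugs and physiotherapy can each break that null without any contribution from the plate. The protocol gives no control group, reference value or performance threshold against which a change could be judged. If the p-value is taken as the answer to the aim, recovery from injury will be reported as efficacy of the plate. The comparative hypothesis cannot be addressed by this test at all.

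Two measurement definitions add to the problem. The aim speaks of pain during jaw movement, but the outcome definition does not carry that condition over. Lateral movement is the distance between the upper and lower midlines, so a midline that is already off-centre at rest is counted as movement. Eligibility is limited to unilateral fractures, where side matters, yet the definition mentions neither side nor resting position. Readings not taken at the visits cannot be recovered by a later analysis plan.

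**Working it through.** **The plan's own figure.** Section VIII gives a minimum of 10 patients at alpha 0.05 and beta 0.05, raised to 14 for dropout. No outcome, effect size, SD or sidedness is stated, so 10 cannot be reproduced. Solved backwards for a two-sided paired t-test, it implies a standardised mean change (mean change divided by SD of change, written dz) of about 1.29. The protocol does not say that the calculation was for pain or movement, so this is for orientation only.

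**Chance of significance with zero plate effect.** Inputs: n = 14, or 10 as the stated minimum; two-sided 0.05 (assumed); dz from causes other than the plate (assumed, over a range). The test statistic follows a noncentral t with n − 1 degrees of freedom and noncentrality dz × √n. For n = 14 the noncentrality is 3.742 × dz, and any observed dz above 0.577 is significant.

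| Assumed dz, not due to the plate | Chance of p<0.05, n = 10 | n = 14 |
|---|---|---|
| 0.5 | 29% | 41% |
| 0.8 | 62% | 79% |
| 1.0 | 80% | 93% |
| 1.5 | 99% | 99.9% |

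As a check, 20,000 simulated trials with the same healing in two arms of 14 and no plate effect gave a between-arm test that stayed at about 5% for every dz from 0 to 2.0. The excess comes from the missing comparator, not from the t-test as such.

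**On the VAS scale (0 to 10, assumed values), n = 14, t = mean fall / (SD/√14), 13 degrees of freedom:**

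- fall 1, SD 2: t = 1/(2/3.742) = 1.87, p = 0.084
- fall 2, SD 2.5: t = 2/(2.5/3.742) = 2.99, p = 0.010
- fall 3, SD 2: t = 3/(2/3.742) = 5.61, p = 0.00008

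These p-values apply if the observed mean and SD equal the assumed ones. The table gives the corresponding chances over repeated studies (dz 0.5, 0.8 and 1.5).

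**Lateral movement.** Assume true excursions of 8 mm to each side and a resting midline offset of 2 mm. The midline-to-midline distance then reads 8 + 2 = 10 mm on one side and 8 − 2 = 6 mm on the other. If surgery removes the offset, both read 8 mm: each reading changes by 2 mm although the jaw moves no further than before.

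**The case against.** The strongest reply is that the protocol promises less than the concern supposes. The research question is descriptive, pain and movement are secondary, no sentence says that a pre/post p-value will be taken as proof, and the visit pair may be settled in an analysis plan that is not at hand. The same test sentence also covers ramus height, where a paired comparison of the two sides is natural. This stands as far as it goes, and the unnamed pair is not a fault in itself. But the aim does say efficacy and the hypothesis is comparative. Whichever visits are paired, a within-arm change cannot be assigned to the plate.

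A reader might infer that the test would be significant whatever the plate does. The documents do not support that. They give no size for the change, and at dz 0.5 the chance is 41%. At days 3 and 7 the result may go the other way, because section VI lists pain, edema and difficulty chewing as consequences of surgery. The medication is headed as immediate post-operative with no duration, so cover at those visits is likely but not stated.

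A reader might also take the Background's remark on the cited randomised trial, "they concluded that both treatment options carry promising outcomes", as evidence that recovery does not depend on treatment. The next sentence reports better function after surgery in everything except occlusion, and the Background names pain as the commonest complaint after closed management. That trial compared two treatments and says nothing about untreated healing.

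Nor does the text say that the VAS is scored at rest, or that lateral movement is read in one direction only. What can be said is that the definitions leave both open.

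**Conclusion.** The point holds for the secondary outcomes. A significant change in pain or movement at 1 or 3 months is likely from healing, medication and physiotherapy alone if that change is moderate to large: 79% to 99.9% with 14 patients for an assumed dz of 0.8 to 1.5, but only 41% at 0.5. Such a result cannot support the efficacy aim or the comparative hypothesis. At days 3 and 7 the direction is uncertain. This rests on reading the dependent t-test as pre-operative against follow-up, on two-sided 0.05, and on assumed changes, since the protocol states none.

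It should not be extended to the whole study. The primary outcomes are read on CT immediately after surgery, before healing or analgesia could act on them. The two measurement points are matters of definition: the VAS condition stated in the aim is missing from the outcome list, and the midline distance includes any resting offset.

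**What to change.** 1. In section IX, state that pain and mandibular movements will be reported at each visit as estimates with 95% confidence intervals, descriptively, and that no efficacy or comparative conclusion will be drawn from a within-patient p-value. The 3-month level should not be called an efficacy read-out either, since without a reference value it reflects healing just as a change score does.
2. In section VIII, define the VAS as scored during jaw movement, in line with the aim in section IV.
3. In section VIII, define lateral excursion as measured to the right and to the left from the resting midline. Describe the difference between sides at 3 months, identifying patients with concomitant facial or mandibular fractures, whom section III admits and in whom that difference may have other causes.

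The cost is wording plus a second ruler reading at visits already planned; no extra visit or arm is needed. The price is that the pre/post p-value is no longer offered as evidence for the plate. The change does not make the study comparative.

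### Section IX assigns all discrete data to a chi-square test, but this single-arm study of 14 patients states no comparison for which the ordinary test would be valid

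*Protocol*

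**What the plan says.** Section IX (Statistical Analysis) has two rules. For continuous data: "Regarding the continuous date, the T dependent test will be used to assess the statistical data". For discrete data: "Regarding the discrete data, Chi Square test will be used to assess the statistical data significance, using SPSS Software". It names no grouping factor, no reference value and no paired version of the chi-square test.

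The design is stated elsewhere:

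- Abstract: "This Single arm study will include 14 cases of trauma having mandibular sub condylar fractures".
- Section III, PICOTS table: the comparator cell holds only a dash. The outcome row reads "Pain, posterior facial height, anatomic reduction, mouth deviation".
- Section V (Hypothesis): "Delta plate doesn't provide an added advantage over the other Osteosynthesis methods of Sub condylar fixation". No rate is given for any other method.
- Section VIII, Pre-operative Assessment: "All patients will undergo clinical evaluation of pain, mandible deviation on opening and closing, measurement of mandibular movements".
- Section VIII, Follow up: "Follow up notes will be taken on day three, day seven, one month and Three months postoperatively". For the CT outcomes: "Radiograph will be taken immediately post-operative".

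**The concern.** An ordinary chi-square test needs either independent groups or a stated reference distribution, and this protocol supplies neither. The one comparison that the longitudinal design readily offers is within patients, between visits, and there the test's independence assumption fails. The two rules in Section IX therefore do not match: continuous data get a paired test, while discrete data get one that, in its ordinary form, is unpaired.

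At stake is whether a p-value for a discrete outcome means what it appears to mean. Used between visits, the unpaired test sees only the two visit totals and not how many patients improved or worsened. For an outcome read once, it has no comparison to make.

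**Working it through.** **Step 1. Possible uses of the ordinary chi-square test, against the design.**

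| Use | Needs | What the protocol gives |
|---|---|---|
| Comparison of groups | Independent groups | One arm, no comparator |
| Goodness of fit | A reference proportion | None; the hypothesis mentions other methods without a rate |
| Association within the arm | A planned subgroup factor | Valid in principle, but none is planned |
| Comparison between visits | Independent readings | The same patients, read again |

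**Step 2. Which outcomes could be discrete.** Ramus height (CT), pain (visual analogue scale) and mandibular movements (ruler) are measured quantities. Anatomic reduction has no stated scale and one post-operative CT. Mouth deviation is in the PICOTS outcome row and the pre-operative examination. It is not among the primary and secondary outcomes of Section IV or the clinical outcomes listed under Follow up, and its scale is not given. It is a candidate for a between-visit test only if it is recorded as yes/no and examined again after surgery.

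**Step 3. Effect of ignoring the pairing.** The only input from the protocol is n = 14. The proportions, counts and phi are assumptions, because the protocol gives none. There is no figure in the plan to reproduce on this point.

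For visit totals A and B out of n:

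- Pearson chi-square, no continuity correction: (A − B)² × 2n / [(A + B)(2n − A − B)], 1 df.
- McNemar, with b improving and c worsening: asymptotic (b − c)² / (b + c), 1 df; mid-p = 2·P(X ≤ min(b, c)) − P(X = min(b, c)), with X binomial(b + c, ½).

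*10/14 to 5/14.* Pearson: 25 × 28 / (15 × 13) = 3.590, p = 0.058, whatever the pairing.

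- 5 improve, 0 worsen (phi 0.47): mid-p = 2/32 − 1/32 = 0.031; asymptotic 25/5 = 5, p = 0.025; exact 2/32 = 0.0625.
- 6 improve, 1 worsens (phi 0.14): mid-p = 2 × 8/128 − 7/128 = 0.070.

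So one pairing with non-negative phi changes the 5% verdict on mid-p and the other does not.

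*14/14 to 10/14.* The totals force 4 improving and 0 worsening. Pearson: 16 × 28 / (24 × 4) = 4.667, p = 0.031. Asymptotic McNemar: 16/4 = 4, p = 0.046. Mid-p: 2/16 − 1/16 = 0.0625. The verdict differs on mid-p but not on the asymptotic form. The smallest expected count here is 4/2 = 2, so the large-sample approximation is itself weak.

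*10/14 to 4/14.* Pearson: 36 × 28 / (14 × 14) = 5.143, p = 0.023. With non-negative phi, mid-p is 0.016 (6–0) or 0.039 (7–1), so the verdict does not change.

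**Step 4. Size with no true change.** Exact enumeration of all paired 2×2 outcomes at n = 14, two-sided 5%, true proportion 30–70% at both visits:

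| phi | Pearson | McNemar asymptotic | McNemar mid-p | McNemar exact |
|---|---|---|---|---|
| 0 | 4.1–5.2% | 4.5–4.9% | 3.2–3.7% | 1.3–1.7% |
| 0.3 | 1.6–2.1% | 4.7–5.1% | 1.8–2.5% | 0.5–0.8% |
| 0.6 | 0.2–0.3% | 2.0–2.8% | 0.4–0.7% | 0.05–0.12% |

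**Step 5. Power, same enumeration.**

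| Change | phi | Pearson | Asymptotic | Mid-p | Exact |
|---|---|---|---|---|---|
| 30% to 70% | 0 | 54% | 52% | 51% | 38% |
| 30% to 70% | 0.3 | 55% | 72% | 64% | 47% |
| 90% to 50% | 0 | 69% | 62% | 58% | 44% |
| 90% to 50% | 0.2 | 70% | 75% | 66% | 48% |

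McNemar's test gains when phi is clearly positive, except in its exact form. Near phi 0 Pearson has the higher power.

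**The case against.** **The wording is generic.** McNemar's test is itself a chi-square test, and the neighbouring sentence chooses a dependent test, so the author may have meant a paired form. If so, naming it settles the between-visit part. It would not help an outcome read once, which still has neither a comparison nor a reference value.

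**This is detail for a statistical analysis plan.** Outcome scales and visit pairs could indeed be left to one, and their absence is not criticised here. But the protocol does fix a test for all discrete data, and in its ordinary form that test does not fit the stated design.

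**No outcome is shown to be affected.** This stands. A reader might infer that the primary outcome of anatomic reduction will be tested invalidly. The document does not support that, because its scale is not stated. Nor does any passage schedule mouth deviation after surgery or call it yes/no.

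**The consequence is modest.** This also stands. A reader might infer inflated false positives; in the null scenarios above, Pearson's size never goes materially above 5%. A reader might also point to much larger gaps: 10/14 to 4/14 with 10 improving and 4 worsening gives mid-p 0.118 against 0.023, and 10/14 to 5/14 with 9 and 4 gives 0.180 against 0.058. These need within-patient phi of −1.00 and −0.85. In the first, every patient switches status. They are arithmetically possible but not a fair measure of the problem.

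**Conclusion.** The point holds in a limited form. As written, the chi-square rule has no valid comparison in this single-arm study: no groups, no reference proportion and no planned subgroup analysis. Used between visits, it would ignore the pairing that the plan recognises for continuous data.

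The statistical cost is mainly conservatism. Size falls from about 4–5% at phi 0 to about 2% at phi 0.3 and 0.2–0.3% at phi 0.6, and some 5% verdicts change in either direction depending on the form of McNemar's test. These sizes rest on assumed proportions of 30–70%, assumed phi and all 14 patients contributing both readings. The between-visit part is conditional on some discrete measure being read at two visits, which the protocol does not state. The mismatch between rule and design does not depend on these assumptions.

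**What to change.** Replace the chi-square sentence in Section IX with:

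*Each discrete outcome will be reported as number and proportion with an exact 95% CI; a yes/no measure compared between two visits named in advance, in the same patients, will be tested with one pre-specified form of McNemar's test.*

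Which form to name is the investigator's choice, made before the data are seen, because the forms differ visibly at n = 14. If all visits are to be compared together, Cochran's Q or a repeated-measures model would be needed instead. If a paired chi-square was always meant, naming it settles the between-visit part.

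For an outcome read once, the exact (Clopper-Pearson) interval is the informative result: 14/14 gives 77–100%, and 12/14 gives 57–98%.

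The cost is one sentence, with no extra patients or data. The downsides are that an outcome read once has no p-value, and that McNemar's test, especially the exact form, can have less power than the ordinary chi-square when correlation is near 0. Mid-p is itself conservative (size 1.8–2.5% at phi 0.3).
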